#### 9.4.2 Statistical model, hypothesis, and method of analysis

The data analysis for the current study will be primarily descriptive. Therefore there are no a-priori hypothesis being tested.

## 9.4.3 **Primary Efficacy Analysis**

The primary efficacy outcome will be assessed by the proportion of patients on LCZ696 97 mg sacubitril / 103 mg valsartan bid at 6 months of treatment. Ninety five percent (95%) confidence intervals will be calculated for the estimate of this proportion in order to assess precision and make inferences to the target population.

## 9.4.4 Secondary Efficacy Analyses

Similarly, for the secondary efficacy outcomes, the proportion of patients on LCZ696 97 mg sacubitril / 103 mg valsartan bid at 12 months, the proportion of patients requiring down titration, and the proportion of patients treated in accordance to guideline recommended doses of beta blockers and MRAs, will also be assessed for precision with the 95% Confidence Intervals.

The number of down titrations during the 12 month treatment periods will be described with a Poisson distribution and the incidence density rate (IDR) as the number of dose reductions per 100 person – month of follow up.

The change in the Six Minute Walk Test from baseline to 6 and 12 months of treatment will be assessed with the 95% confidence intervals and with the Student's t-test for paired observations.

The time to LCZ696 up-titration to 97 mg sacubitril / 103 mg valsartan bid and the duration on treatment for each dose will be assessed with the Kaplan Meier estimator of the survival function.

#### 9.4.6 Handling of missing values/censoring/discontinuations

There will be no replacement or imputation of missing values. All analysis will be conducted on observed cases only. For patients lost to follow up after achieving the LCZ696 dose of 97 mg sacubitril / 103 mg valsartan bid, the conservative approach will be used according to which they will be considered as not staying on treatment. A sensitivity analysis will be conducted to assess the impact of this assumption by using only the PP patients.

Confidential

## 9.4.7 Supportive analyses

Not Applicable.

## 9.5 Analysis of secondary variables

#### 9.5.1 Efficacy variables

Not Applicable.

#### 9.5.2 Safety variables

Adverse events (AEs) will be classified according to the MedDRA dictionary of terms (Version 18.1 or newer) and summarized using the total number of AEs, the total number and percentage of patients who experience an AE overall, and the number and percent of patients who experience an AE within each system organ class (SOC) and preferred terms (PTs) within individual SOCs. Analysis of the number of patients who experience each AE will be performed in the following manner: patients experiencing the same AE multiple times will only be counted once for the corresponding PT; similarly, if a patient experiences multiple AEs within the same SOC, that patient will be counted only once for that SOC. A similar table will be produced for serious adverse events (SAEs), AEs with reasonable probability to be related to the study treatment (definitely related, probably related, possibly related), and SAEs with reasonable probability to be related to the study treatment. Finally, a summary table reporting the breakdown of the total number of AEs by seriousness (serious, non-serious), severity (mild, moderate, severe), relationship to study medication (definitely related, probably related, possibly related, unlikely related, definitely not related), action taken, and outcome will be prepared. The Safety Analysis will be carried out on the Safety Population only.

# 9.5.3 **Resource utilization**

Not Applicable.

# 9.5.5 **Pharmacokinetics**

Not Applicable.

#### 9.5.6 Pharmacogenetics/pharmacogenomics

Not Applicable.

9.5.7 **Biomarkers** 

Not Applicable.

9.5.8 **PK/PD** 

Not Applicable.

# 9.6 Sample size calculation

The primary outcome measure for the current study will be the proportion of patients on 97 mg sacubitril / 103 mg valsartan bid of LCZ696 at 6 months of treatment. The data from clinical trials have shown that at 12 weeks (3 months) approximately 80% of patients have achieved this dose. In this current real – life study of 6 months (primary endpoint) a reasonable estimate of patients achieving this dose would be 70%.

Confidential

Given that this is a single cohort, prospective study in which all patients are receiving the same treatment and the objective is to describe the proportion of patients reaching 97 mg sacubitril / 103 mg valsartan bid LCZ696, sample size requirements are based on the precision of the estimate. This is assessed with the 95% confidence interval. A reasonable level of precision is one with a 95% confidence interval width ( $\omega$ ) that is between 5 and 15% of the point estimate. With 300 patients enrolled in the study, the 95% Confidence Interval width will be ± 5.2% which is equivalent to 7.4% of the point estimate of 70%, with upper and lower limits of 64.8% – 75.2% respectively. This is within the limits of reasonable precision.

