# 3 Investigational plan

#### 3.1 Study design

This will be a multi-center, open label, prospective post-approval (phase IV) study. Patients with HFrEF that are eligible to be treated with LCZ696 as per the product monograph will be enrolled in the study. The study patients will be enrolled at Canadian community cardiologists and IM specialists that treat patients with HFrEF. Follow up will be for 12

months with assessments at baseline, week 2, week 4, month 3, month 6 and month 12. The primary endpoint will be assessed after 6 months of follow-up.

Confidential

Potentially eligible patients with HFrEF will be invited to participate in the study and will be asked to sign an informed consent after the purpose, duration and requirements of the study have been explained to them. Treatment with ACEIs will be discontinued for 36 hours and then replaced with LCZ696 at 24 mg sacubitril / 26 mg valsartan bid. NO washout period is need for patients previously treated on ARBs. The dose of LCZ696 will be increased to 49 mg sacubitril / 51 mg valsartan bid within 2-4 weeks of enrolment and to 97 mg sacubitril / 103 mg valsartan bid within 2-4 weeks from the first up titration to 49 mg sacubitril / 51 mg valsartan bid as tolerated by the patient and in accordance to the product monograph (Figure 3-1). All other medications will be used as they were prior to the enrolment in the study; however, the treating physicians may modify the dose of nitrates, CCBs,  $\alpha$ -blockers, and diuretics in order to facilitate tolerability of increased LCZ696 doses. Down titration of LCZ696 from the higher doses may be considered, as per the product monograph for patients that experience tolerability issues including, but not limited to, symptomatic hypotension or hyperkalemia.

\* Titration scheme in the study protocol will reflect approved Canadian product monograph

\* LCZ696 50 mg bid is the equivalent of 24 mgsacubitril / 26 mg valsartan bid

\* LCZ696 100 mg bid is the equivalent of 49 mg sacubitril / 51 mg valsartan bid

\* LCZ696 200 mg bid is the equivalent of 97 mg sacubitril / 103 mg valsartan bid

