#### 5.5.6 **Permitted dose adjustments and interruptions of study treatment**

For patients who are unable to tolerate the protocol-specified dosing scheme, dose adjustments and interruptions of LCZ696 are permitted in order to keep the patient on study drug. Attempt will be made to maintain patients on LCZ696 at 97 mg sacubitril / 103 mg valsartan bid. If in the opinion of the investigator, the patient does not tolerate the highest dose of LCZ696, the investigator should consider whether non disease-modifying medication (such as nitrates, CCBs,  $\alpha$ -blockers, and diuretics) can be reduced temporarily to permit up-titration and maintenance of a proven efficacious dose of LCZ696.

Attempt should be made to maintain patients on the proposed study drug dose level for as long as duration as possible throughout the trial. If, however, in the opinion of the investigator, the patient does not tolerate the target dose of study drug, the investigator should consider whether non-disease-modifying medication (e.g., CCBs, diuretics, nitrates,  $\alpha$ -blockers) can be reduced to rectify the situation, before considering to reduce the dose of the study drug to the next lower dose level. Also, the investigator may adjust doses of disease-modifying medications if it is believed that they are the most likely cause of the adverse effect. If adjustment/elimination of concomitant medications is not possible or does

not alleviate the side effects of concern, the investigator may opt to down-titrate the dose of the study drug to the next lower level (either 24 mg sacubitril / 26 mg valsartan or 49 mg sacubitril / 51 mg valsartan depending which dose the patient is taking). If needed, the study drug may be stopped completely, but the patient should then discontinue the trial.

Confidential

These changes must be recorded on the Dosage Administration Record CRF.

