2.5.2 Statistical hypothesis, model, and method of analysis

The data analysis will be primarily descriptive. Therefore, there is no a-priori hypothesis being tested.

The primary efficacy outcome will be assessed by the proportion of patients on LCZ696 97 mg sacubitril / 103 mg valsartan bid at 6 months of treatment. 95% confidence interval using binomial proportion will be calculated for the estimate of the proportion in order to assess precision and make inferences to the target population.

Novartis	For business use only	Page 13
SAP		PARASAIL / LCZ696BCA02

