2.15 Interim analysis

An interim analysis may be performed after 50 patients have reached 12 weeks of treatment, and at any

time during the study as long as it does not impact the study completion.

3 Sample size calculation

The primary outcome measure for the current study will be the proportion of patients on 97 mg sacubitril / 103 mg valsartan bid of LCZ696 at 6 months of treatment. The data from clinical trials have shown that at 12 weeks (3 months) approximately 80% of patients have achieved this dose. In this current real – life study of 6 months (primary endpoint) a reasonable estimate of patients achieving this dose would be 70%.

Given that this is a single cohort, prospective study in which all patients are receiving the same treatment and the objective is to describe the proportion of patients reaching 97 mg sacubitril / 103 mg valsartan bid LCZ696, sample size requirements are based on the precision of the estimate. This is assessed with the 95% confidence interval. A reasonable level of precision is one with a 95% confidence interval width (ω) that is between 5 and 15% of the point estimate. With 300 patients enrolled in the study, the 95% Confidence Interval width will be \pm 5.2% which is equivalent to 7.4% of the point estimate of 70%, with upper and lower limits of 64.8% – 75.2% respectively. This is within the limits of reasonable precision.

4 Change to protocol specified analyses

Not applicable.

5 Appendix

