5.4 Statistical models

5.4.1 Primary anlysis

For the proportion and percentage along with 95% confidence limits estimated using normal approximation (binomial proportion), statistical programmer may use the following code:

```
<Sample code>
proc freq data= <xxx>;
tables <xxx> / binomial;
run;
```

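### Does the sample-size section overstate its precision by setting the half-width of the 95% CI against a rule written for the width?

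*Protocol*

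**What the plan says.** Protocol 9.6 bases the sample size on the precision of the primary proportion, the share of patients on the target dose at 6 months, which it expects to be 70%. The rule reads "A reasonable level of precision is one with a 95% confidence interval width" (denoted ω) "that is between 5 and 15% of the point estimate". The section then states that with 300 patients "the 95% Confidence Interval width will be ± 5.2% which is equivalent to 7.4% of the point estimate of 70" per cent, gives limits of 64.8% and 75.2%, and concludes that this is reasonable precision. SAP section 3 repeats the paragraph, including "which is equivalent to 7.4% of the point estimate of 70%, with upper and lower limits of 64.8% – 75.2% respectively".

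For the analysis itself, SAP 2.5.2 says that a "95% confidence interval using binomial proportion will be calculated for the estimate of the proportion". SAP 5.4.1 specifies the normal approximation, with the sample code line "tables <xxx> / binomial". Protocol 9.4.2 and SAP 2.5.2 both say that the analysis is mainly descriptive and that no hypothesis is tested in advance.

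**The concern.** The width of a confidence interval normally means the distance from its lower to its upper limit. Read that way, the rule governs one quantity and the figure set against it is another, half as large. Precision is the only argument offered for 300 patients. A reader who sees 7.4% beside a 15% ceiling would infer that the study is about twice as precise as it needs to be. On the literal reading it only just qualifies, and a few patients fewer or a slightly lower proportion would take it over the ceiling.

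A second worry goes with this. The interval is a simple binomial one used to make inferences to the target population. Protocol 3.1 says "This will be a multi-center, open label, prospective post-approval (phase IV) study", and under Protocol 5.5.6 "the investigator may opt to down-titrate the dose of the study drug to the next lower level". Dosing could therefore vary by site, and neither document mentions correlation within sites. If it exists, the simple interval would be too narrow.

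**Working it through.** Inputs: expected proportion p = 0.70, n = 300, 95% confidence and the 5 to 15% band (Protocol 9.6, SAP section 3); normal-approximation interval (SAP 5.4.1), so z = 1.96.

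1. **The plan's own figure.** Half-width = 1.96 × √(0.70 × 0.30 / 300) = 0.0519, or 5.2 points. Relative to the estimate, 0.05186 / 0.70 = 7.4%. The limits are 70 − 5.2 = 64.8% and 70 + 5.2 = 75.2%. All printed figures reproduce.

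2. **Full width.** 2 × 0.05186 = 0.1037, or 10.4 points; 0.1037 / 0.70 = 14.8%. The rounded limits give (75.2 − 64.8) / 70 = 14.9%.

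3. **Against the rule.** 7.4% and 14.8% both lie between 5 and 15%. The statement that precision is reasonable holds on either reading.

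4. **Slack on the full-width reading.** 15.0 − 14.8 = about 0.2 percentage points.
   - At p = 0.70 the ceiling needs n ≥ 4 × 1.96² × 0.30 / (0.70 × 0.15²) = 292.7, so 293 patients (292 gives 15.02%, 293 gives 14.99%).
   - With n = 300 the ceiling holds for p of about 69.5% or more (65% gives 16.6%).
   - These are one-way values. They do not form a joint condition.

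5. **The rule is a band, so both ends count.** At p = 0.70:
   - Half-width reading, ceiling: 1.96² × 0.30 / (0.70 × 0.15²) = 73.2. Floor: 1.96² × 0.30 / (0.70 × 0.05²) = 658.6. The range is n = 74 to 658, and 300 is well inside it.
   - Full-width reading: four times those values, 292.7 and 2,634.2. The range is n = 293 to 2,634, and 300 is at its edge.

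   This does not prove what was intended. It does fit the half-width reading, which is how the section itself applies the word.

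6. **Site effect.** On the full-width reading, a variance inflation above 300 / 292.7 = 1.025 would pass 15%. Whether such inflation exists cannot be judged. The documents give no number of sites, no patients per site and no intra-site correlation. The two passages cited show a multi-centre study in which an investigator may lower the dose for a patient who does not tolerate it. They do not show variation between sites.

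**The case for a change.** The strongest case for a change is that the rule names the width, the figure applied to it is the half-width, and nothing else supports 300. On the literal rule the margin is fragile on the plan's own terms:

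- The calculation counts 300 enrolled. The protocol glossary puts enrolment at consent, while the primary denominator is patients with at least one dose. Eight consented but untreated patients would leave 292 and a full width of 15.02%.
- Withdrawn patients are not replaced, so the per-protocol set will be smaller.
- Patients lost to follow-up after reaching the target dose count as not staying on it, which can only lower the proportion. At the plan's own lower limit of 64.8%, the full width would be 2 × 1.96 × √(0.648 × 0.352 / 300) / 0.648 = 16.7% of the estimate.
- An exact interval at 210 of 300 would give 15.2%.

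The arithmetic stands, and so does the criticism of the wording. What does not follow is a consequence. The 15% ceiling is a planning convention. It is not a success criterion, and no documented decision is taken when it is crossed. The observed interval will be reported whatever its width. The exact interval is not the planned method. A miss of a few tenths of a percentage point against a rule of thumb would not alter how the estimate is read. Nor is the reader left with only the 7.4%, because both limits stand in the same sentence.

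The request for a site-clustered interval can be considered separately, and it is weaker. With no sized effect and an unchanged primary interval, it is an optional extra and corrects nothing in the plan.

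**Conclusion.** No change to the plan is called for. The section uses the word width for the ± value, and that is a slip of terminology. At 70% and 300 patients the half-width is 5.2 points (7.4% of the estimate) and the full width 10.4 points (14.8%). Both satisfy the 5 to 15% rule, so the stated conclusion and the sample size stand. On the full-width reading the slack is only about 0.2 percentage points, which is worth knowing when the section is read, but no analysis or decision rests on it. Clearer wording would not change what the trial does or reports. This conclusion assumes the planning values of 70% and 300 analysed patients and the normal-approximation interval in SAP 5.4.1. It makes no claim about the size of any site effect, which the documents do not allow to be estimated.

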# 10 Ethical considerations

# 10.1 **Regulatory and ethical compliance**

This clinical study was designed and shall be implemented and reported in accordance with the ICH Harmonized Tripartite Guidelines for Good Clinical Practice, with applicable local regulations (including European Directive 2001/20/EC, US Code of Federal Regulations Title 21, and Japanese Ministry of Health, Labor, and Welfare), and with the ethical principles laid down in the Declaration of Helsinki.

# 10.2 Informed consent procedures

Eligible patients may only be included in the study after providing written, IRB/IECapproved informed consent, or, if incapable of doing so, after such consent has been provided by a legally acceptable representative of the patient. In cases where the patient's representative gives consent, the patient should be informed about the study to the extent possible given his/her understanding. Informed consent must be obtained before conducting any study-specific procedures (i.e. all of the procedures described in the protocol). The process of obtaining informed consent should be documented in the patient source documents.

Confidential

Novartis will provide to investigators in a separate document a proposed informed consent form that complies with the ICH GCP guideline and regulatory requirements and is considered appropriate for this study. Any changes to the proposed consent form suggested by the investigator must be agreed to by Novartis before submission to the IRB/IEC, and a copy of the approved version must be provided to the Novartis monitor after IRB/IEC approval.

Women of child bearing potential should be informed that taking the study treatment may involve unknown risks to the fetus if pregnancy were to occur during the study and agree that in order to participate in the study they must adhere to the contraception requirement for the duration of the study. If there is any question that the patient will not reliably comply, they should not be entered in the study.

# 10.3 **Responsibilities of the investigator and IRB/IEC**

The protocol and the proposed informed consent form must be reviewed and approved by a properly constituted Institutional Review Board/Independent Ethics Committee/Research Ethics Board (IRB/IEC) before study start. A signed and dated statement that the protocol and informed consent have been approved by the IRB/IEC must be given to Novartis before study initiation. Prior to study start, the investigator is required to sign a protocol signature page confirming his/her agreement to conduct the study in accordance with these documents and all of the instructions and procedures found in this protocol and to give access to all relevant data and records to Novartis monitors, auditors, Novartis Clinical Quality Assurance representatives, designated agents of Novartis, IRBs/IECs, and regulatory authorities as required. If an inspection of the clinical site is requested by a regulatory authority, the investigator must inform Novartis immediately that this request has been made.

#### 10.4 **Publication of study protocol and results**

Novartis assures that the key design elements of this protocol will be posted in a publicly accessible database such as clinicaltrials.gov. In addition, upon study completion and finalization of the study report the results of this trial will be either submitted for publication and/or posted in a publicly accessible database of clinical trial results.

# 11 **Protocol adherence**

Investigators ascertain they will apply due diligence to avoid protocol deviations. Under no circumstances should the investigator contact Novartis or its agents, if any, monitoring the trial to request approval of a protocol deviation, as requests to approve deviations will not be granted.

This protocol defines the study objectives, the study procedures and the data to be collected on study participants. Under no circumstances should an investigator collect additional data or conduct any additional procedures for any research related purpose involving any investigational drugs.

If the investigator feels a protocol deviation would improve the conduct of the study this must be considered a protocol amendment, and unless such an amendment is agreed upon by Novartis and approved by the IRB/IEC it cannot be implemented. All significant protocol deviations will be recorded and reported in the CSR.

#### 11.1 **Protocol Amendments**

Any change or addition to the protocol can only be made in a written protocol amendment that must be approved by Novartis, Health Authorities where required, and the IRB/IEC. Only amendments that are required for patient safety may be implemented prior to IRB/IEC approval. Notwithstanding the need for approval of formal protocol amendments, the investigator is expected to take any immediate action required for the safety of any patient included in this study, even if this action represents a deviation from the protocol. In such cases, Novartis should be notified of this action and the IRB/IEC at the study site should be informed within 10 working days or less, if required by local regulations.

# 13 Appendix 1: Clinically notable laboratory values and vital signs

Clinically notable laboratory abnormalities for selected tests based on a percent change from baseline:

#### Hematology

RBC count	>50% increase, >20% decrease
Hemoglobin	>50% increase, >20% decrease
Hematocrit	>50% increase, >20% decrease
WBC count	>50% increase, >50% decrease
Platelet count	>75% increase, >50% decrease
Blood Chemistry	
ALT (SGPT)	>150% increase
AST (SGOT)	>150% increase
BUN	>50% increase
Creatinine	>50% increase
Total bilirubin	>100% increase
СРК	>300% increase
Alkaline phosphatase	>100% increase
Potassium	>20% increase, >20% decrease
Chloride	>10% increase, >10% decrease
Calcium	>10% increase, >10% decrease
Uric acid	>50% increase

